**Table A5. Oxygenation parameters**

		Baseline		Day 4		Day 7		Day 14	
		n	Mean±SD	n	Mean±SD	n	Mean±SD	n	Mean±SD
Mean airway pressure (cm H 2 O)									
	Aspirin	n	xx.x ± x.x	n	xx.x ± x.x	n	xx.x ± x.x	n	xx.x ± x.x
	Placebo	n	xx.x ± x.x	n	xx.x ± x.x	n	xx.x ± x.x	n	xx.x ± x.x
	p-value #				0.xxx		0.xxx		0.xxx
Expiratory Tidal volume (ml/kg PBW)									
	Aspirin	n	xx.x ± x.x	n	xx.x ± x.x	n	xx.x ± x.x	n	xx.x ± x.x
	Placebo	n	xx.x ± x.x	n	xx.x ± x.x	n	xx.x ± x.x	n	xx.x ± x.x
	p-value #				0.xxx		0.xxx		0.xxx
PEEP (cmH 2 O)									
	Aspirin	n	xx.x ± x.x	n	xx.x ± x.x	n	xx.x ± x.x	n	xx.x ± x.x
	Placebo	n	xx.x ± x.x	n	xx.x ± x.x	n	xx.x ± x.x	n	xx.x ± x.x
	p-value #				0.xxx		0.xxx		0.xxx
Plateau pressure (cm H 2 O)									
	Aspirin	n	xx.x ± x.x	n	xx.x ± x.x	n	xx.x ± x.x	n	xx.x ± x.x
	Placebo	n	xx.x ± x.x	n	xx.x ± x.x	n	xx.x ± x.x	n	xx.x ± x.x
	p-value #				0.xxx		0.xxx		0.xxx
pH									
	Aspirin	n	xx.x ± x.x	n	xx.x ± x.x	n	xx.x ± x.x	n	xx.x ± x.x
	Placebo	n	xx.x ± x.x	n	xx.x ± x.x	n	xx.x ± x.x	n	xx.x ± x.x
	p-value #				0.xxx		0.xxx		0.xxx
pCO 2									
	Aspirin	n	xx.x ± x.x	n	xx.x ± x.x	n	xx.x ± x.x	n	xx.x ± x.x
	Placebo	n	xx.x ± x.x	n	xx.x ± x.x	n	xx.x ± x.x	n	xx.x ± x.x
	p-value #				0.xxx		0.xxx		0.xxx
Standard Base Excess									
	Aspirin	n	xx.x ± x.x	n	xx.x ± x.x	n	xx.x ± x.x	n	xx.x ± x.x
	Placebo	n	xx.x ± x.x	n	xx.x ± x.x	n	xx.x ± x.x	n	xx.x ± x.x
	p-value #				0.xxx		0.xxx		0.xxx
Lactate mmol/L									
	Aspirin	n	xx.x ± x.x	n	xx.x ± x.x	n	xx.x ± x.x	n	xx.x ± x.x
	Placebo	n	xx.x ± x.x	n	xx.x ± x.x	n	xx.x ± x.x	n	xx.x ± x.x
	p-value #				0.xxx		0.xxx		0.xxx

# p values for ANCOVA or mixed model

**Table A6. Fluid Balance**

		Baseline		Day 4		Day 7		Day 14	
		n	Mean±SD	n	Mean±SD	n	Mean±SD	n	Mean±SD
Total Fluid In (ml)									
	Aspirin	n	xx.x ± x.x	n	xx.x ± x.x	n	xx.x ± x.x	n	xx.x ± x.x
	Placebo	n	xx.x ± x.x	n	xx.x ± x.x	n	xx.x ± x.x	n	xx.x ± x.x
Total Fluid Out (ml)									
	Aspirin	n	xx.x ± x.x	n	xx.x ± x.x	n	xx.x ± x.x	n	xx.x ± x.x
	Placebo	n	xx.x ± x.x	n	xx.x ± x.x	n	xx.x ± x.x	n	xx.x ± x.x

Fluid Balance							
	Aspirin	n	xx.x ± x.x	n	xx.x ± x.x	n	xx.x ± x.x
	Placebo	n	xx.x ± x.x	n	xx.x ± x.x	n	xx.x ± x.x
	p-value #			0.xxx		0.xxx	

# p values for ANCOVA or mixed model

**Table A7. Summary statistics for clinical Laboratory Assessments, by Treatment Group**

		Baseline		Day 4		Day 7		Day 14	
		n	Mean±SD	n	Mean±SD	n	Mean±SD	n	Mean±SD
Highest ALT (U/L)									
	Aspirin	n	xx.x ± x.x	n	xx.x ± x.x	n	xx.x ± x.x	n	xx.x ± x.x
	Placebo	n	xx.x ± x.x	n	xx.x ± x.x	n	xx.x ± x.x	n	xx.x ± x.x
	p-value #			0.xxx		0.xxx		0.xxx	
Highest AST (U/L)									
	Aspirin	n	xx.x ± x.x	n	xx.x ± x.x	n	xx.x ± x.x	n	xx.x ± x.x
	Placebo	n	xx.x ± x.x	n	xx.x ± x.x	n	xx.x ± x.x	n	xx.x ± x.x
	p-value #			0.xxx		0.xxx		0.xxx	
Highest ALP (U/L)									
	Aspirin	n	xx.x ± x.x	n	xx.x ± x.x	n	xx.x ± x.x	n	xx.x ± x.x
	Placebo	n	xx.x ± x.x	n	xx.x ± x.x	n	xx.x ± x.x	n	xx.x ± x.x
	p-value #			0.xxx		0.xxx		0.xxx	
Highest CRP mmol/L									
	Aspirin	n	xx.x ± x.x	n	xx.x ± x.x	n	xx.x ± x.x	n	xx.x ± x.x
	Placebo	n	xx.x ± x.x	n	xx.x ± x.x	n	xx.x ± x.x	n	xx.x ± x.x
	p-value #			0.xxx		0.xxx		0.xxx	
PT (s)									
	Aspirin	n	xx.x ± x.x	n	xx.x ± x.x	n	xx.x ± x.x	n	xx.x ± x.x
	Placebo	n	xx.x ± x.x	n	xx.x ± x.x	n	xx.x ± x.x	n	xx.x ± x.x
	p-value #			0.xxx		0.xxx		0.xxx	
APTT (s)									
	Aspirin	n	xx.x ± x.x	n	xx.x ± x.x	n	xx.x ± x.x	n	xx.x ± x.x
	Placebo	n	xx.x ± x.x	n	xx.x ± x.x	n	xx.x ± x.x	n	xx.x ± x.x
	p-value #			0.xxx		0.xxx		0.xxx	
Fibrinogen (g/l)									
	Aspirin	n	xx.x ± x.x	n	xx.x ± x.x	n	xx.x ± x.x	n	xx.x ± x.x
	Placebo	n	xx.x ± x.x	n	xx.x ± x.x	n	xx.x ± x.x	n	xx.x ± x.x
	p-value #1			0.xxx		0.xxx		0.xxx	
Hb (g/L)									
	Aspirin	n	xx.x ± x.x	n	xx.x ± x.x	n	xx.x ± x.x	n	xx.x ± x.x
	Placebo	n	xx.x ± x.x	n	xx.x ± x.x	n	xx.x ± x.x	n	xx.x ± x.x
	p-value #			0.xxx		0.xxx		0.xxx	
WBC (x10^9/L)									
	Aspirin	n	xx.x ± x.x	n	xx.x ± x.x	n	xx.x ± x.x	n	xx.x ± x.x

		Baseline		Day 4		Day 7		Day 14	
		n	Mean±SD	n	Mean±SD	n	Mean±SD	n	Mean±SD
	Placebo	n	xx.x ± x.x	n	xx.x ± x.x	n	xx.x ± x.x	n	xx.x ± x.x
	p-value #			0.xxx		0.xxx		0.xxx	
Neutrophils(x10^9/L)									
	Aspirin	n	xx.x ± x.x	n	xx.x ± x.x	n	xx.x ± x.x	n	xx.x ± x.x
	Placebo	n	xx.x ± x.x	n	xx.x ± x.x	n	xx.x ± x.x	n	xx.x ± x.x
	p-value #			0.xxx		0.xxx		0.xxx	
Highest Urea mmol/L									
	Aspirin	n	xx.x ± x.x	n	xx.x ± x.x	n	xx.x ± x.x	n	xx.x ± x.x
	Placebo	n	xx.x ± x.x	n	xx.x ± x.x	n	xx.x ± x.x	n	xx.x ± x.x
	p-value #			0.xxx		0.xxx		0.xxx	
Lowest eGFR mL/min									
	Aspirin	n	xx.x ± x.x	n	xx.x ± x.x	n	xx.x ± x.x	n	xx.x ± x.x
	Placebo	n	xx.x ± x.x	n	xx.x ± x.x	n	xx.x ± x.x	n	xx.x ± x.x
	p-value #			0.xxx		0.xxx		0.xxx	

# p values for ANCOVA or mixed model

**Table A 2.. Adverse events/reactions (AE/AR), serious adverse events/reactions (SAE/SAR) & suspected unexpected serious adverse reactions**

		Number of Events			Number of Patients				
		Total	Aspirin	Placebo	Total N=<n>	Aspirin N=<n>	Placebo N=<n>	RR (95%I)	p-values
AE/AR, SAE/SAR and SUSAR	Total number of adverse events (AEs)	n	n	n	n (%)	n (%)	n (%)	x.xx (x.xx to x.xx)	x.xx
	Total number of adverse reactions (ARs)	n	n	n	n (%)	n (%)	n (%)	x.xx (x.xx to x.xx)	x.xx
	Total number of serious adverse events (SAEs)	n	n	n	n (%)	n (%)	n (%)	x.xx (x.xx to x.xx)	x.xx
	Total number of serious adverse reactions (SARs)	n	n	n	n (%)	n (%)	n (%)	x.xx (x.xx to x.xx)	x.xx
	Total number of events related to study drug and unexpected (SUSAR)	n	n	n	n (%)	n (%)	n (%)	x.xx (x.xx to x.xx)	x.xx
AEs	Blood and lymphatic system disorders	n	n	n	n (%)	n (%)	n (%)	x.xx (x.xx to x.xx)	x.xx
	Cardiac disorders	n	n	n	n (%)	n (%)	n (%)	x.xx (x.xx to x.xx)	x.xx
	Gastrointestinal disorders	n	n	n	n (%)	n (%)	n (%)	x.xx (x.xx to x.xx)	x.xx
	Hepatobiliary disorders	n	n	n	n (%)	n (%)	n (%)	x.xx (x.xx to x.xx)	x.xx
	General disorders and administration site conditions	n	n	n	n (%)	n (%)	n (%)	x.xx (x.xx to x.xx)	x.xx
	Infections and infestations	n	n	n	n (%)	n (%)	n (%)	x.xx (x.xx to x.xx)	x.xx
	Injury, poisoning and procedural complications	n	n	n	n (%)	n (%)	n (%)	x.xx (x.xx to x.xx)	x.xx
	Musculoskeletal and connective tissue disorders/Elevated Creatinine Kinase	n	n	n	n (%)	n (%)	n (%)	x.xx (x.xx to x.xx)	x.xx
	Investigations	n	n	n	n (%)	n (%)	n (%)	x.xx (x.xx to x.xx)	x.xx
	Nervous system disorders	n	n	n	n (%)	n (%)	n (%)	x.xx (x.xx to x.xx)	x.xx
	Renal and urinary disorders	n	n	n	n (%)	n (%)	n (%)	x.xx (x.xx to x.xx)	x.xx
	Respiratory, thoracic and mediastinal disorders	n	n	n	n (%)	n (%)	n (%)	x.xx (x.xx to x.xx)	x.xx
Skin and subcutaneous tissue disorders	n	n	n	n (%)	n (%)	n (%)	x.xx (x.xx to x.xx)	x.xx	
SAEs	Blood and lymphatic system disorders	n	n	n	n (%)	n (%)	n (%)	x.xx (x.xx to x.xx)	x.xx
	Cardiac disorders	n	n	n	n (%)	n (%)	n (%)	x.xx (x.xx to x.xx)	x.xx
	Gastrointestinal disorders	n	n	n	n (%)	n (%)	n (%)	x.xx (x.xx to x.xx)	x.xx
	Hepatobiliary disorders	n	n	n	n (%)	n (%)	n (%)	x.xx (x.xx to x.xx)	x.xx
	General disorders and administration site conditions	n	n	n	n (%)	n (%)	n (%)	x.xx (x.xx to x.xx)	x.xx
	Infections and infestations	n	n	n	n (%)	n (%)	n (%)	x.xx (x.xx to x.xx)	x.xx
	Injury, poisoning and procedural complications	n	n	n	n (%)	n (%)	n (%)	x.xx (x.xx to x.xx)	x.xx

	Number of Events			Number of Patients				
	Total	Aspirin	Placebo	Total N=<n>	Aspirin N=<n>	Placebo N=<n>	RR (95%I)	p-values
Musculoskeletal and connective tissue disorders/Elevated Creatinine Kinase	n	n	n	n (%)	n (%)	n (%)	x.xx (x.xx to x.xx)	x.xx
Investigations	n	n	n	n (%)	n (%)	n (%)	x.xx (x.xx to x.xx)	x.xx
Nervous system disorders	n	n	n	n (%)	n (%)	n (%)	x.xx (x.xx to x.xx)	x.xx
Renal and urinary disorders	n	n	n	n (%)	n (%)	n (%)	x.xx (x.xx to x.xx)	x.xx
Respiratory, thoracic and mediastinal disorders	n	n	n	n (%)	n (%)	n (%)	x.xx (x.xx to x.xx)	x.xx
Skin and subcutaneous tissue disorders	n	n	n	n (%)	n (%)	n (%)	x.xx (x.xx to x.xx)	x.xx

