# 1. BACKGROUND AND DESIGN

The trial hypothesis under investigation is that treatment with aspirin is safe and improves important surrogate clinical outcomes in adult patients with ARDS.

The objective of the trial is

1. To conduct a prospective randomised, double-blind, allocation concealed, placebo-controlled phase 2 trial of aspirin as a treatment for ARDS.
2. To study the biological effects of aspirin on pulmonary and systemic
  - a. inflammatory responses,
  - b. epithelial and endothelial function and injury and
  - c. lipid inflammatory mediators

Subjects will be randomised to receive aspirin 75mg capsule or a placebo capsule enterally for up to 14 days. Subjects will be randomised in a 1:1 ratio using blocks of variable size. The first dose of the study drug will ideally be administered within 4 hours of randomisation and subsequent doses will be as close to 10 am as possible starting on the following calendar day.

Patients will be eligible to participate in the study if they fulfil the following criteria:

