## **Exclusion criteria:**

1. More than 72 hours from the onset of ARDS.

2. Age < 16 years.
3. Patient is known to be pregnant.
4. Participation in a clinical trial of an investigational medicinal product within 30 days.
5. Current treatment with aspirin or within the past 4 weeks.
6. Platelet count <  $50 \times 10^9/l$ .
7. Haemophilia or other haemorrhagic disorder or concurrent therapeutic anticoagulant therapy.
8. History of aspirin sensitive asthma or nasal polyps associated with asthma.
9. Active or history of recurrent peptic ulcer and/ or gastric/ intestinal haemorrhage or other kinds of bleeding such as cerebrovascular haemorrhage.
10. Traumatic brain injury.
11. Active gout.
12. Currently receiving methotrexate.
13. Severe chronic liver disease with Child-Pugh score > 12.
14. Known hypersensitivity or previous adverse reaction to salicylic acid compounds or prostaglandin synthetase inhibitors.
15. Physician decision that aspirin is required for proven indication.
16. Contraindication to enteral drug administration, e.g. patients with mechanical bowel obstruction.
17. Treatment withdrawal imminent within 24 hours.
18. Consent declined.

The trial is summarised in Figure 1.

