## 5. SAMPLE SIZE CALCULATIONS

The primary outcome measure is the difference in OI at day 7, between aspirin and placebo treated groups. Based on our data from a recently completed clinical trial in ARDS, the mean (standard deviation; SD) OI at day 7 in patients with ARDS is 62 (51) cmH2O/kPa. A sample size of 56 subjects (28 in each group) will have 80% power at a two-tailed significance level of 0.05 to detect a clinically significant difference of 39 cmH2O/kPa in OI between groups. In a previous phase 2 study of similar size, we have found that an intervention can demonstrate a change in OI of a similar magnitude confirming a treatment effect of this size can be achieved.

Although we anticipate few withdrawals or loss to follow-up we have allowed for this in the sample size calculation. In our previous single centre study of simvastatin in ARDS there were no withdrawals. In a multi-centre UK study of pulmonary artery catheters in ICU patients

(PAC-Man), no patients were lost to follow up, and only 3% withdrew consent after recovering competency. This is in keeping with our local data. Therefore, a drop-out rate of 5% has been estimated and the study will require a total of 60 patients (30 in each group). All calculations assume 80% power at a two-tailed significance level of 0.05.

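### The adverse event analysis never compares bleeding between arms; one pre-specified row for any bleeding event would supply that estimate, though with low power at 30 per arm

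*SAP*

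**What the plan says.** Section 1 sets out the hypothesis that "treatment with aspirin is safe and improves important surrogate clinical outcomes" in adults with ARDS. Safety is also secondary outcome 4 in Section 2.2.

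Three exclusion criteria in Section 1 concern bleeding: a low platelet count (6), a haemorrhagic disorder or therapeutic anticoagulation (7), and "Active or history of recurrent peptic ulcer and/ or gastric/ intestinal haemorrhage or other kinds of bleeding such as cerebrovascular haemorrhage" (9).

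Section 6 plans the number of events and the number (%) of patients for AEs, ARs, SAEs, SARs and SUSARs. The arms are compared by Fisher's exact test and a proportion test, with relative risks and 95% CIs; tests are two-sided at 0.05. Section 7.5 lists AEs, SAEs, SUSARs and death by arm.

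The adverse events table in Appendix 1 (it follows the laboratory table) has 5 rows of totals, then 13 organ-class rows for AEs and the same 13 for SAEs, such as "Gastrointestinal disorders". Each row has a relative risk and a p-value. No row, endpoint or test in the SAP concerns bleeding across organ classes.

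**The concern.** Bleeding is a key hazard here. That is an inference from exclusions 6, 7 and 9; the SAP does not rank its expected harms. Bleeds could be coded under gastrointestinal, nervous system, respiratory, renal and urinary, blood, skin, or injury and procedural rows, and each of those rows also holds events that have nothing to do with bleeding. Followed as written, the plan produces 26 organ-class comparisons and no estimate of how many patients bled in each arm.

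At stake is the safety half of the trial's question. A set of thin, mixed rows without a significant difference could be read as reassurance on bleeding when bleeding was not examined. If bleeds were grouped only after unblinding, the choice of terms would be open to the charge of being post hoc.

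**Working it through.** **The plan's own figure.** Section 5 states that "A sample size of 56 subjects (28 in each group) will have 80% power at a two-tailed significance level of 0.05" for a "clinically significant difference of 39" cmH2O/kPa, with SD 51. The t-test calculation gives 27.8, so 28 per arm, with power 80.2%. Dividing 56 by 0.95 gives 58.9, so 59, and 60 for equal arms. The figure reproduces, but it concerns the oxygenation index at day 7. The SAP gives neither a bleeding rate nor a power for safety.

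**Inputs for bleeding.**
- From the SAP: 30 per arm (Section 5), two-sided 0.05, Fisher's exact test and a proportion test (Section 6).
- Assumed: risk of any bleed 5% on placebo and 25% or 30% on aspirin; bleeds split evenly over k = 3, 4 or 5 rows; rows independent; rows contain bleeds only. Only significant results towards more bleeding on aspirin are counted.

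**Method.** Pooled power is the sum of binomial probabilities over all pairs of counts (0 to 30 per arm) with p ≤ 0.05. For split rows, the row risks are the pooled risks divided by k, which gives a single-row power q. The chance that at least one row is significant is 1 − (1 − q)^k.

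Example, 5% v 25%, k = 3, Fisher: row risks are 0.05/3 = 1.67% and 0.25/3 = 8.33%, q = 0.0219, and 1 − (1 − 0.0219)³ = 6.4%. For k = 5, q = 0.0024 and 1 − (1 − 0.0024)⁵ = 1.2%.

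| Assumed risk | Test | Pooled row | At least one of 3 to 5 rows |
|---|---|---|---|
| 5% v 25% | Fisher | 44% | 6% to 1% |
| 5% v 25% | Proportion, uncorrected | 63% | 40% to 21% |
| 5% v 30% | Fisher | 63% | 13% to 3% |
| 5% v 30% | Proportion, uncorrected | 78% | 55% to 33% |

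**Counts.** By Fisher, a row with 30 per arm needs at least 6 v 0, 8 v 1 or 9 v 2 patients. A row of 2 v 0 gives p = 0.49, 3 v 0 gives 0.24 and 4 v 0 gives 0.11; by the proportion test, 4 v 0 gives 0.038.

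**Uneven split.** Suppose that 60% of bleeds are gastrointestinal and that row holds nothing else. Its power is 15% (Fisher) or 39% (proportion) at 5% v 25%, and 26% or 53% at 5% v 30%.

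**Unrelated events in the row.** Now suppose that 20% of each arm also has a non-bleeding gastrointestinal event. The row risk becomes 1 − (1 − 0.20)(1 − 0.6p). For p = 5% this is 1 − 0.80 × 0.97 = 22.4%; for p = 30% it is 1 − 0.80 × 0.82 = 34.4%. Fisher power falls from 26% to about 11%, against 63% pooled.

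**Limits of a pooled row.** By Fisher it misses 5% v 25% in 100 − 44 = 56% of trials and 5% v 20% in about 76%. It reaches 80% power only at about 5% v 35.5%. Take 8/30 v 1/30 (Fisher p = 0.026). The risk difference is 26.7% − 3.3%, about 23 percentage points. The relative risk is 8.0, with 95% CI exp(ln 8 ± 1.96 × √(1/8 − 1/30 + 1/1 − 1/30)), that is 1.07 to 60. With one event fewer on aspirin, 7 v 1, p = 0.052.

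**The case against.** A reader might infer that splitting the rows means a bleeding excess would almost certainly be missed. The document does not support that, for three reasons.
- Section 6 plans a proportion test beside Fisher's, and under it the split rows would show 5% v 25% in 21-40% of trials.
- The even split is an assumption, and bleeding concentrated in one row would be easier to see.
- Trial size is a large part of the problem, because the pooled row also misses many real excesses.

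All three points stand. They limit the size of the loss but do not supply a bleeding comparison. A significant mixed row would still not say that bleeding was the cause.

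Other safety content exists. The AR and SAR totals cover all sites; Hb, PT, APTT and fibrinogen are compared by arm; stopping for a drug-related event is tabulated; and the DMEC sees safety data by arm. None of these counts patients who bled. The AR and SAR totals mix bleeds with other reactions and take only those judged drug-related, laboratory means are group averages, and DMEC review is not the final comparison.

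The tables are headed as example drafts, and the protocol, not shown here, may define bleeding events. But Sections 6 and 7.5 add no bleeding comparison either, and how safety data are compared between arms is for the SAP to fix. The SAP contradicts nothing on this point. What is open is an analysis choice, not an error of fact.

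**Conclusion.** The point holds as an omission with a cheap remedy. The plan as written gives no estimate of bleeding by arm, although its hypothesis covers safety and its exclusions recognise bleeding as a hazard. At 30 per arm, splitting cuts the chance of a significant result at 5% v 25% from about 44% to 1-6% by Fisher, and from about 63% to 21-40% by the proportion test. At 5% v 30% the corresponding falls are from 63% to 3-13% and from 78% to 33-55%.

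These figures rest on assumed rates, an even split over 3 to 5 rows, independent rows and rows free of other events. The last assumption favours the split rows. A pooled row has low power for moderate excesses, so its value is a direct, pre-specified estimate with a confidence interval. It does not secure detection.

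**What to change.** Add one row for any bleeding event (patients with at least one, all sites) to the AE block and one to the SAE block of the adverse events table, and name the comparison in Sections 6 and 7.5. Fix the list of qualifying terms, and flag events against it, blind to arm before database lock. Report n (%) by arm, the risk difference and the relative risk, each with a 95% CI. State that power is low, so that a non-significant result is not read as absence of harm.

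The cost is two table rows and a blinded pass through the recorded adverse event terms. The downside is having to agree the term list before lock. How completely bleeds are recorded depends on reporting rules in the protocol, which should be checked when the list is drawn up.

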**Table A 3. Age & Kidney Function**

Status	All patients	Treatment Group		T-test p-values
		Aspirin	Placebo	
Number (%) of patients Age>65	n (xx.x%)	n (xx.x%)	n (xx.x%)	0.xxx
Number (%) of patients aged > 65 starting RRT after randomisation	n	n	n	0.xxx
Baseline				
EGFR *	xx.x ±xx.x	xx.x ±xx.x	xx.x ±xx.x	0.xxx
Creatinine	xx.x ±xx.x	xx.x ±xx.x	xx.x ±xx.x	0.xxx
Change from baseline to day 7				
EGFR *	xx.x ±xx.x	xx.x ±xx.x	xx.x ±xx.x	0.xxx
Creatinine	xx.x ±xx.x	xx.x ±xx.x	xx.x ±xx.x	0.xxx

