### 3.4 Data verification

Data verification, consistency and range checks will have been performed at the data entry stage by the CTU, as well as checks for missing data (copies can be found in the Trial Master File). Additional range, consistency and missing data checks will be performed, as appropriate, when the analysis is performed (and when the datasets for analysis are constructed). All variables will be examined for unusual, outlying, unlabelled or inconsistent values.

Given the thorough nature of our follow-up procedure we expect the issue of missing data to be relatively minimal. We anticipate high compliance with initial data collection as this is close to the time of patient registration. If any data is missing imputation will not be done.

Any problems with trial data will be queried with the Trial Managers, Data Managers, or statisticians, as appropriate. If possible, data queries will be resolved, although it is accepted that due to administrative reasons and data availability a small number of problems will continue to exist. This will be minimised.

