## 6. ANALYSIS PRINCIPLES

Primary outcome measure is the OI at day 7. Unadjusted (primary analysis) and adjusted analysis will be carried out to test whether there is a statistically significant difference between the aspirin & placebo groups. Secondary analysis will be carried out, if the day 7 OI values are missing, using last value carry forward method.

Secondary outcome measures are OI, CRs, PF ratio, and SOFA score at day 4, 7, 14 and safety. Unadjusted and adjusted analysis will be carried out on OI, CRs, PF ratio, SOFA score, to test whether there is a statistically significant difference between the groups.

Unadjusted analysis will be carried out using Independent sample t-test. Adjusted analysis will be carried out using ANCOVA or [mixed modelling technique](#), based the number of data points available at each time point. Estimates & 95% confidence interval will be reported.

The number of AE, ARs, SAE, SARs, SUSARs and number (%) of patient experiencing the events will be reported. Fisher's exact test and proportion test will be used to check whether incidences of adverse events differ between the groups. Relative risk and 95% CI will be reported.

Exploratory analysis on mediators will be carried out using student t-tests or non-parametric alternative and Fishers Exact Test, presented by day where applicable. The estimates & 95% CIs will be reported. Statistical diagnostic methods will be used to check for violations of the assumptions, and transformations will be performed if required. For binary outcome measures, risk ratios and associated 95% CI will be calculated. Survival analysis technique will be used for time-to-event data. Median survival time & 95% CI will be estimated using Kaplan-Meier estimation method and the Kaplan-Meier plots will be presented. In all time-to-event analyses, patients that did not experience the event in question (e.g. death) were censored on the date last seen or 90 days. The equality of survivorship function of aspirin & placebo group will be tested

for significance using a log-rank  $\chi^2$  test. Hazard ratios (HRs) & 95% CIs will be reported if the proportionality assumption holds.

Correlations between changes in the biological markers measured and physiological and clinical outcomes will be assessed by appropriate graphical and statistical methods including Pearson's (or Spearman's) correlation coefficient.

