A secondary analysis excluding patients identified to have aspirin resistance will also be undertaken.

Analyses will be conducted according to intention to treat principle. All statistical tests will be 2-sided and a p-value of 0.05 will be considered as statistically significant, unless adjustment for multiple testing was needed. A single analysis is planned at the end of the trial. Every effort will be made to minimise missing baseline and outcome data in this trial. Any ad-hoc analysis will be reported as per the regulatory requirement.

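### Table A 3 counts new RRT only in patients over 65, puts counts under a t-test, and averages day-7 creatinine change with no rule for patients on RRT

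*SAP*

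**What the plan says.** Table A 3 in Appendix 1 (Age & Kidney Function) has columns for all patients, aspirin and placebo, and one p-value column headed "T-test p-values". Its rows are:

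- the number of patients over 65;
- "Number (%) of patients aged > 65 starting RRT after randomisation", whose cells show n only although the label promises a percentage;
- baseline eGFR and creatinine, as mean ± SD;
- eGFR and creatinine under "Change from baseline to day 7", also as mean ± SD.

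The eGFR rows carry an asterisk whose note is not visible in the text at hand. The creatinine rows carry none. No rule is given for values taken on RRT or for patients already on RRT at baseline.

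Three statements elsewhere bear on the table:

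- Section 6 on analysis sets: "Analyses will be conducted according to intention to treat principle". No exclusion for RRT is stated.
- Section 3.4 on missing values: "If any data is missing imputation will not be done".
- Section 6 on tests: "Fisher's exact test and proportion test will be used to check whether incidences of adverse events differ between the groups", and "For binary outcome measures, risk ratios and associated 95% CI will be calculated".

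The adverse-event table in Appendix 1 has a row "Renal and urinary disorders" for AEs and another for SAEs, at all ages, with n (%), risk ratio, 95% CI and p-value. The laboratory table shows lowest eGFR and highest urea at days 4, 7 and 14, with no RRT rule there either.

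**The concern.** There are three defects in one table.

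1. **RRT count.** Starting RRT is the clearest sign of renal failure that the table plans to show, but only over-65s are counted. No all-age count appears elsewhere in the SAP.
2. **Creatinine change.** RRT removes creatinine, so a day-7 value on RRT does not measure kidney function. Averaging such values with the rest mixes the effect of RRT into the comparison between arms. The all-age RRT count that would let a reader interpret the mean is missing.
3. **Test.** The t-test heading covers two rows of counts, contrary to Section 6.

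Safety is part of the trial hypothesis in Section 1, and Table A 3 is the SAP's only table devoted to kidney function. A renal difference could be partly uncounted and its mean creatinine contrast distorted.

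**Working it through.** The SAP states no figure for renal outcomes, so there is none to reproduce. The documents supply the arm size of 30 (Section 5). RRT rates, creatinine values and the share of patients over 65 are all assumptions.

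**Creatinine change.** Suppose a of 30 patients in one arm and b of 30 in the other are on new RRT at day 7, each with on-RRT creatinine minus baseline equal to c, and all other patients do not change. The arm means are a·c/30 and b·c/30, so the difference is (a − b)·c/30. With a = 5 and b = 1 this is 4c/30:

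| Assumed baseline → on RRT (umol/L) | c | Arm with 5/30 | Arm with 1/30 | Difference |
|---|---|---|---|---|
| 80 → 150 | +70 | +11.7 | +2.3 | +9.3 |
| 120 → 150 | +30 | +5.0 | +1.0 | +4.0 |
| 200 → 100 | -100 | -16.7 | -3.3 | -13.3 |
| fall of 180 | -180 | -30 | -6 | -24 |

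The sign follows c. If creatinine on RRT stays above baseline, the arm with more RRT still looks worse, though by less than it would had RRT not lowered the values. If it falls below baseline, that arm looks better.

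**Age limit.** Take 9 against 3 RRT starts among 30 per arm, spread evenly over age. If 30% to 50% of patients are over 65, the row shows about 2.7 to 4.5 against 0.9 to 1.5, so 50% to 70% of starts go uncounted. For true rates of 40% against 10%, the exact power of Fisher's test is 0.71 with 30 per arm, 0.33 with 15 and 0.14 with 9.

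**Test on counts.** Two-sided p-values on the same 0/1 data:

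| Counts | t-test | Fisher | Uncorrected chi-square |
|---|---|---|---|
| 5/30 v 0/30 | 0.019 | 0.052 | 0.020 |
| 5/30 v 1/30 | 0.088 | 0.195 | 0.085 |
| 4/12 v 0/12 | 0.028 | 0.093 | 0.028 |
| 8/30 v 2/30 | 0.038 | 0.080 | 0.038 |

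The t-test is smaller than Fisher's in every row, and in three of the four the two fall on opposite sides of 0.05.

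**The case against.** **Direction of the creatinine effect.** A reader might infer that the arm with more kidney failure would look improved. The documents do not support that as a certainty. Change is measured from baseline, and RRT lowers creatinine from its peak, not necessarily below baseline. A fall of 180 umol/L needs a baseline above 180, which means kidneys already impaired at entry. The SAP gives no baseline creatinine, on-RRT value or RRT rate. This objection stands, so the claim is only that the contrast can be blunted or reversed.

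**The t-test.** It might be read as part of a masking problem. It is not: its p-values are smaller than Fisher's, so it flags an imbalance more readily. It also nearly matches an uncorrected chi-square, and Section 6 names a proportion test beside Fisher's. What stands is a mismatch between table and text that can change which side of 0.05 a result falls on.

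**Other renal reporting.** The renal AE and SAE rows cover all ages and do not depend on creatinine, and total SOFA is a secondary outcome. It would be wrong to say that renal harm has no other route into the report. But those AE/SAE rows depend on an event being reported and coded, and neither they nor total SOFA isolate RRT.

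**Standing of the table.** Section 2.2 assesses safety through adverse events, Section 7 does not refer to this table, and the appendix is headed as example drafts. That limits the weight of the point. However, the body of the SAP contains no RRT rule to fall back on.

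**eGFR.** The note to the asterisk may have been lost when the PDF was read and may already deal with RRT. The point on averaging is therefore firm only for creatinine.

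**Conclusion.** The point holds in a limited form and should be corrected. The text itself shows that the RRT count is restricted to over-65s with no all-age count elsewhere, and that count rows sit under a t-test heading contrary to Section 6. That the creatinine means include patients on RRT is an inference from the all-patients column, intention to treat and the absence of any exclusion, but it is the natural reading.

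The size depends on assumed inputs. At 5/30 against 1/30 new RRT, the difference for the arm with more RRT runs from +9.3 to -24 umol/L, according to whether on-RRT creatinine ends above or below baseline. If 30% to 50% of patients are over 65, the age limit omits 50% to 70% of RRT starts. The wrong-test point is separate: 0.019 against 0.052 at 5/30 v 0/30. The primary outcome is not affected.

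**What to change.** In Table A 3:

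1. Report RRT starts after randomisation as n/N (%) for all randomised patients not on RRT at baseline, with over-65s as a sub-row. Use Fisher's exact test and a risk ratio with 95% CI, in line with Section 6.
2. Replace the t-test on both count rows.
3. Show creatinine change to day 7 for patients not on RRT at baseline or day 7, with n per arm, placed next to the RRT count and labelled descriptive. Do the same for eGFR change unless the asterisk note already covers it.

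The cost is one table shell. RRT start, creatinine and eGFR are already planned for it; RRT status at baseline and day 7 must be available to define the groups. The downside is that off-RRT means describe a subset selected after randomisation, so they are not a randomised comparison. That is why they should be descriptive and read beside the RRT count.
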